5.2 Agent Administration

5.2.1 Isoquercetin or placebo

Depending on assigned Cohort during Phase II or randomization in Phase III each capsules will contain 250 mg isoquercetin versus placebo. Isoquercetin will be supplied as oral capsules. Capsules will be consumed once daily (2 or 4 capsules depending on cohort designation). Dose modifications will not be

made. Capsules will be dispensed from the research pharmacy on C1D1 and again on C2D1. The capsules will be packaged as a 30 day supply (to allow for unexpected occurrences such as dropped capsule).

Capsules may be swallowed with or without food. The capsules can be opened and the contents mixed with a small portion of soft acidic food such as apple sauce, puree of carrots, or pumpkin puree (Phase II only). Missed doses must be taken within four hours of scheduled dose. If longer than four hours, or if dose vomited, skip dose. Subjects will keep a drug diary that will be provided to them by the study team. Subjects will be instructed to return any unused drug. The unused returns will be counted by pharmacy and destroyed on-site per policy.

5.3 Duration of Therapy

Duration of therapy will be 56 days (+/- 7 days inclusion of windows) or until one of the following criteria applies:

- Intercurrent illness that prevents further administration of treatment,
- Unacceptable adverse event(s),
- Participant demonstrates an inability or unwillingness to comply with the oral medication regimen and/or documentation requirements
- Participant decides to withdraw from the study, or general or specific changes in the participant's condition render the participant unacceptable for further treatment in the opinion of the treating investigator.
- Grade 3 or 4 hemorrhage and/or Symptomatic bleeding in a critical area or organ such as intracranial, intraspinal, intraocular, retroperitoneal, intra-articular or pericardial, or intramuscular with compartment syndrome, and/or bleeding causing a fall in hemoglobin level >2 g/L or bleeding leading to a transfusion of > 2 units of packed red blood cells.
- Proximal deep vein thrombosis or pulmonary embolism
- Condition requiring therapeutic anticoagulation
- Prophylactic heparin or low molecular weight heparin for greater than 7 consecutive days

5.4 Duration of Follow Up

Following completion of treatment, only the cause and date of death will be recorded. Participants removed from study for unacceptable adverse events will be followed until resolution or stabilization of the adverse event. Participants removed from active treatment will be followed for survival.

5.5 Criteria for Removal from Study

Participants will be removed from study when any of the criteria listed in Section 5.3 applies. The reason for study removal and the date the participant was removed must be documented in the study-specific case report form (CRF). Alternative care options will be discussed with the participant.

In the event of unusual or life-threatening complications, participating investigators must immediately notify the Principal Investigator, at

6 EXPECTED TOXICITIES AND DOSING DELAYS/DOSE MODIFICATIONS

Dose delays and modifications will be made using the following recommendations. Toxicity assessments will be done using the CTEP latest Version of the NCI Common Terminology Criteria for Adverse Events (CTCAE) which is identified and located on the CTEP website at: http://ctep.cancer.gov/protocolDevelopment/electronic_applications/ctc.htm.

If possible, symptoms should be managed symptomatically. In the case of toxicity, appropriate medical treatment should be used (including anti-emetics, anti-diarrheals, etc.).

All adverse events experienced by participants will be collected from the time of the first dose of study treatment, through the study and until the final study visit. Participants continuing to experience toxicity at the off study visit may be contacted for additional assessments until the toxicity has resolved or is deemed irreversible.

6.1 Anticipated Toxicities

A list of the adverse events and potential risks associated with the agents administered in this study appear below and will determine whether dose delays and modifications will be made or whether the event requires expedited reporting **in addition** to routine reporting.

A number of clinical trials have shown minimal to no adverse effects from oral quercetin (the parent compound of isoquercetin). In several studies conducted to investigate various potential effects of quercetin on immune function, risk factors for heart disease, or exercise-induced oxidative stress among others, the ingestion of quercetin by healthy subjects (males and females, group sizes ranging from 11 to 63; mean ages for treatment and control groups ranged from 20 to 46 years) at a daily dose of 600 to 1000 mg/day for periods of 1 to 6 weeks was not associated with any reports of adverse effects⁴⁸⁻⁵² A randomized, double-blind, placebo-controlled 12-week study was conducted in which subjects (male and female, ages 18 to 85 years) were randomized to consume a placebo (n = 335) or 500 (n=334) or 1,000 (n=333) mg of quercetin daily. There were no significant toxicities or metabolic changes between the groups.⁵³

Intravenous administration of quercetin can be associated with nephrotoxicity. Doses up to 11.4 mg/kg body weight (equivalent of 694 mg in a 60 kg patient) were associated with transient flushing and mild pain at the injection site⁵⁴. At the higher dose levels of up to 54.1 mg/kg body weight (equivalent to 10,000 mg orally), grade 1-4 nephrotoxicity was described, as well as dyspnea and emesis.

Despite the potential antithrombotic activity of quercetin and flavonoids, hemorrhage has not been described as a toxicity in clinical studies.

The supplied capsules contain ascorbic acid (62 mg) and niacin (5 mg) to prevent oxidation and improve absorption of isoquercetin. The recommended daily allowance of niacin is between 14 and 16 mg. Higher doses of niacin (between 300 mg and 6000 mg daily) are prescribed for hyperlipidemia and can be associated with flushing as well as other side effects such as hepatotoxicity. At physiologic dosing, side effects attributable to niacin would be unexpected. Similarly, ascorbic acid supplementation is not associated with significant toxicity. There are case reports of hemolytic anemia in patients with G6PD deficiency receiving extreme doses (several grams) of ascorbic acid.

6.1.1 Adverse Event Lists(s) for Isoquercetin (with ascorbic acid and niacin)

Mild hypotension (decrease in systolic blood pressure of less than 10mmHg) Mild nausea or diarrhea Hemolysis (rare) Hemorrhage Headache

6.2 Toxicity Management

Hemorrhage

- No modification: CTCAE grade 1
- HOLD: CTCAE grade 2 hemorrhage

Hold isoquercetin until resolution of grade 2 hemorrhage. The maximum number of consecutive days that isoquercetin can be held is 10 days before the participant must be taken off study. A participant may only hold isoquercetin for one ten day period. If a second grade 2 hemorrhage develops the participant must be taken off study.

• **Discontinue:** CTCAE grade 3-4 hemorrhage or otherwise meets criteria for major hemorrhage such as requiring transfusion 2 units PRBC, postoperative interventional radiology, endoscopic or operative intervention or life threatening consequences including spontaneous bleeding at critical site (intracranial, pericardial, retroperitoneal, intraocular, intraspinal)

In cases of suspected isoquercetin toxicity (non-hematologic only):
Grade 2: if toxicity is tolerable to patient, maintain at same dose. If toxicity is intolerable to the patient, then interrupt quercetin until recovery to grade <1
Grade 3 : interrupt until grade <1
Grade 4 : discontinue isoquercetin

6.3 Dose Modifications/Delays

For non-hematologic toxicity, see section 6.2 for dose delays.

For thrombocytopenia: Grade 3 (platelet count <50,000 /mcl). Hold study drug until grade 2. The maximum amount of time that the study drug can be held without withdrawing the participant from the study is 10 days.

7 DRUG FORMULATION AND ADMINISTRATION

7.1 Isoquercetin

7.1.1 **Description**

Isoquercetin, a glucoside form of quercetin, is a naturally occurring flavonol belonging to a broad group of pigmented substances of plant origin known as flavonoids. Flavonoids are a group of polyphenols characterized by a phenyl benzo(γ)pyrone-derived structure, consisting of 2 benzene rings, linked by a heterocyclic pyran or pyrone ring. The chemical name is: 2-(3,4-dihydroxyphenyl)-3,5,7-trihydroxy-4*H*-1-benzopyran-4-one. The molecular formula is C₂₁H₂₀O₁₂ and a molar mass of 464.38 g/mol. It is also known as quercetin-3-O-glucoside CAS Number is 482-35-9.

Isoquercetin undergoes deglycosylation by an extracellular β -glycosidase on the brush border of enterocytes yielding the aglycone.^{24,25} Although the absorption of the related quercetin compounds may differ, all forms of quercetin are metabolized in the enterocyte and liver and circulate as similar glucuronated, sulfated, and methylated conjugates.²⁶⁻²⁸ These conjugates have demonstrated biologic activity^{2,29,30}. The pharmacokinetic study we conducted in healthy adults (isoquercetin 500mg chews), resulted in a median peak concentration of 3.5 μ M and T ¹/₂ of 9 hours. Following metabolism in the liver and/or degradation in the intestine, quercetin is principally excreted as exhaled CO₂ with much smaller amounts found in feces and urine.^{25,34}

There is limited data regarding cytochrome interactions and isoquercetin (see Investigators Brochure for additional details). The data is inconsistent data regarding the interaction of quercetin and metabolism of drugs by cytochrome CYP3A4. The AUC of nifedipine was not altered when co-administered with quercetin nor was the bioavailability of the saquinavir affected (both metabolized by CYP3A4). However, there is some evidence that cyclosporin levels can increase following quercetin administration.¹ Pharmacokinetic profiles of drugs metabolized by other cytochromes (e.g. CYP2C9, CYP2C8) such as warfarin and rosiglitazone do not appear to be influenced by quercetin co-administration. Quercetin does not affect P-gp-mediated efflux as reflected by lack of effect on digoxin pharmacokinetics.¹

7.1.2 Form

Isoquercetin occurs as a greenish-yellow, crystalline solid that is purified from plant sources (>99.5% purity) formulated into immediate release HPMC dark green capsules (size 0).

Both placebo and isoquercetin capsules contain the following: ascorbic acid (62mg), niacin (5mg), magnesium stearate (5mg), colloidal silicon dioxide. The capsules are manufactured and supplied by Pharmavize N.V. Isoquercetin capsules will contain 250 mg isoquercetin.

7.1.3 Storage and Stability

The isoquercetin and placebo capsules are packaged into high density polyethelene bottles and should be kept at room temperature. Stability studies have demonstrated that isoquercetin capsules are stable for at least 2 months and longer term stability studies are ongoing (packaging will be updated accordingly).

7.1.4 Compatibility

No specific compatibility issues

7.1.5 Handling

No specific measures necessary

7.1.6 Availability

Isoquercetin is commercially available but will be supplied free-of-charge from Pharmavize (as will placebo) as a 30 day supply distributed on C1D1 and C2D1 by the local research pharmacy.

7.1.7 Preparation

No specific preparation required.

7.1.8 Administration

Subjects will consume either 2 or 4 capsules daily (depending on cohort allocation). Capsules should be separated by approximately 24 hours.

7.1.9 Ordering

For shipment of isoquercetin, participating sites will contact:

Isoquercetin will be sent directly to the participating hospital pharmacy for disbursement.

7.1.10 Accountability

The investigator, or a responsible party designated by the investigator, must maintain a careful record of the inventory and disposition of the agent (investigational or free of charge) using the NCI Drug Accountability Record or another comparable drug accountability form. (See the CTEP website at http://ctep.cancer.gov/protocolDevelopment for the "Policy and Guidelines for Accountability and Storage of Investigational Agents" or to obtain a copy of the drug accountability form.) Participants will record compliance with study treatment in a drug diary that will be provided to them. The drug diary will be collected and re-dispensed at each study visit.

7.1.11 **Destruction and Return**

At the end of the study, unused supplies of isoquercetin should be destroyed according to institutional policies. Destruction will be documented in the Drug Accountability Record Form.

8 CORRELATIVE/SPECIAL STUDIES

8.1 Pharmacodynamic and Correlative Studies

A total of 10 ml of blood will be drawn into blue top tubes (3.2% citrate) in either two 5ml tubes or one 15ml tube.

CONFIDENTIAL This document is confidential. Do not disclose or use except as authorized. Plasma will be separated at 2100 x G for 20 minutes. First centrifugation should be performed within 1 hour of specimen collection. The plasma layer will be centrifuged a second time at 2100 x G x 20 minutes in a single tube. The plasma supernatant will be transferred to a clean tube leaving the 1ml at the bottom of the tube undisturbed (to be discarded). The transferred plasma sample will be aliquoted (500 μ l) into 1.5ml eppendorf tubes.

Tubes may be stored locally at -80°C and batch shipped on dry ice to CAT IQ Study Team

(BIDMC only) Optional blood draws include an additional 10ml drawn into citrated tubes for platelet aggregometry at time 0 and 4 hours. Tubes will be kept at room temperature for analysis in the [name] laboratory. (see below)

Correlative Studies:

- Tissue factor bearing microparticles (TFMP) will be measured by impedance based flow cytometry in triplicate using internal positive controls. A determination of "high" TFMP is based on concentration greater than two-thirds of samples previously collected from patients with advanced cancer (highest tercile of cancer standards). Plasma samples will be stored at -80oC for up to 5 years following the completion of the study. Additional testing for thrombosis risk factors or laboratory markers of coagulation activation may be performed on these stored samples. (See Appendix E for specimen collection and shipping report)
- Plasma PDI-inhibitory activity: The plasma PDI-inhibitory activity will be measured using a modified DiEGSSG assay.⁵⁵ The exposure of the DiEGSSG probe to exogenous PDI and plasma results in increased fluorescence measured spectrophotometrically and can be used to detect the presence of PDI inhibitor activity.
- D-dimer will be performed in a research laboratory using a commercially available ELISA (Roche Diagnostics).
- Coagulation substrates of PDI. The physiological basis for anticoagulant activity of PDI inhibition continues to be investigated. Proposed mechanisms include altered activity of coagulation factors or inhibitors such as tissue factor or antithrombin. The functional activity of proposed coagulation substrates will be assessed on stored plasma (pending additional funding).
- Platelet aggregometry (BIDMC only) will be performed by standard methodology to assess effect of PDI inhibition on platelet activity at baseline and 4 hours after study drug administration.

9 STUDY CALENDAR

Baseline evaluations are to be conducted within 15 days prior to start of protocol therapy.

All assessments must be performed prior to administration of any study medication. All study assessments and medications should be administered within \pm 7 days of the protocol-specified date, unless otherwise noted.

Event/Procedure	Screening/ Pre- treatment visit	Day 1 (C1D1)	Day 29 (C2D1)	Day 56 or End of Study Treatment	Survival Assessment
Day Range	-15 to 0		+ 2 days	+ 5 days	Q6 months
History Assessments	Х				
Informed Consent	Х				
Inclusion/Exclusion Criteria	Х				
Medical History	Х		х	х	
ECOG Performance Status Score	х		х	х	
Concomitant medication review	Х		Х	х	
Treatment allocation ⁶	Х				
Dispense study drug		х	Х		
Drug Diary Collection ³			х	х	
Safety Assessments					
Physical examination including vital signs	Х		х	х	
Height and Weight	Х				
AE/SAE assessment	Х		х	х	
Assessment of signs and symptoms of VTE and bleeding	х		х	х	
Laboratory Tests					
Complete blood count with diff	Х	х	х	Х	
РТ/РТТ	Х				
Creatinine	Х		Х		
AST/ALT	Х		Х		
Total bilirubin	Х				
Urine HCG ⁴	Х				
Correlative plasma samples (all sites) ¹		x		х	
Correlative plasma samples (BIDMC only)		X5		х	
Imaging					
Bilateral lower extremity ultrasound				х	
Quality of Life Survey ²		Х		х	

CONFIDENTIAL This document is confidential. Do not disclose or use except as authorized. ¹Correlative lab instructions (TFMP) provided in Appendix E
²QOL survey provided in Appendix D
³Drug Diary
⁴If applicable
⁵Optional correlative labs to be drawn at time 0 and 4 hours (see section 7.1)
⁶Phase II treatment allocation is by sequential dosing cohort, Phase III allocation is by randomization

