1.3 Secondary Objectives

- To investigate the cumulative incidence of VTE according to tissue factor bearing microparticle status (and isoquercetin randomization). To evaluate the cumulative incidence of major hemorrhage between the groups of patients treated with isoquercetin versus placebo.
- To assess overall survival according to randomization and tissue factor bearing microparticle status
- To investigate the cumulative incidence of total or symptomatic VTE in all treatment arms (and according to tissue factor bearing microparticle status)
- To study the influence of isoquercetin on TFMP levels and change in TFMP levels over time.
- To evaluate the cumulative incidence of VTE in patients with elevated TFMP as well as very elevated d-dimer (>1500 mcg/L) overall and according to randomization.
- To assess for correlation between complete blood count, ECOG, histology, stage, Ddimer, and levels of tissue factor bearing microparticles
- To investigate the influence of chemotherapy, blood counts, growth factors, ECOG performance status on tissue factor bearing microparticle levels as well as VTE risk.
- Influence of VTE and isoquercetin on Quality of Life (QOL)
- To investigate the association between isoquercetin plasma concentrations, inhibition of protein disulfide isomerase activity, and reduction in D-dimer.
- To evaluate the efficacy of isoquercetin to reduce D-dimer or VTE in cancer patients based on levels of circulating tissue factor bearing microparticles or Khorana risk model
- To compare VTE rates at completion of phase II with historical rates of VTE in similar population

CONFIDENTIAL

This document is confidential. Do not disclose or use except as authorized.

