We recently conducted a pharmacokinetic/pharmacodynamic study to assess the PDIinhibitory activity of isoquercetin in humans. Following an oral dose of isoquercetin (1000 mg capsules), the median peak concentration was 4.45 μ M with a half-life of 8.2 hours. PDI inhibitory activity of plasma was measured using the fluorescent substrate dieosin glutathione disulfide (di-E-GSSG) to liberate a self-quenching N-terminal GSSG residue following cleavage of a disulfide bond.⁷⁻⁹ In all study subjects, we detected significant PDI-inhibitory activity in plasma following the oral administration of isoquercetin 1000 mg capsule.¹⁰

Quercetin as an antithrombotic agent

The antithrombotic potential of flavonoids first garnered attention in the 1990's following the publication of several large epidemiologic studies. In the Zupthen Elderly Study, the group of individuals who consumed over 30 mg of flavonoids daily experienced a nearly 70% reduction in mortality from myocardial infarction (adjusted RR 0.32, 95% CI 0.15-0.71) compared with those individuals who consumed less than 20 mg daily.¹¹ A prospective study of nearly 35,000 postmenopausal women demonstrated that flavonoid consumption reduced both cardiovascular and overall mortality¹² which was also confirmed in a meta-analysis of 7 cohort studies.¹³ Flavonoid consumption has also been linked with a decreased incidence of nonfatal and fatal stroke.^{14,15} Attempts have been made to identify which thrombotic risk factors are modulated with dietary flavonoid consumption but endpoints such as blood pressure, high and lowdensity lipoprotein concentrations, and flow-mediated dilatation have yielded inconsistent results. Flavonoids such as isoquercetin are known to inhibit platelet function in vitro.¹⁶⁻¹⁹ The ingestion of either onion soup or quercetin -4'-O-β-D-glucoside (the predominant quercetin found in onions) inhibited ex vivo platelet aggregation.^{20,21} However there has never been a late stage clinical study on the use of isoquercetin to specifically prevent thrombotic events in humans.

CONFIDENTIAL This document is confidential. Do not disclose or use except as authorized.

Selection of dose:

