The inhibitory IC50 of PDI activity in vitro for isoquercetin metabolites ranges between 3-10uM.² Following the oral administration of isoquercetin (1000 mg) in healthy volunteers, the peak concentration of isoquercetin metabolites in healthy volunteers was 4.45μ M and was associated with 67% inhibition of PDI activity in plasma at 4 hours.¹⁰ Isoquercetin is widely available as a health food supplement and small clinical studies have not demonstrated toxicity. In a pilot trial conducted in 16 patients with mild cognitive impairment, isoquercetin 350 mg and ascorbic acid 400 mg taken for 6 months demonstrated a positive trend in cognitive function without any reported side effects (Investigators Brochure). In another study designed to evaluate the effect of isoquercetin and quercetin 1000 mg daily for two weeks without toxicity.²² Based on in vitro, animal, and human data as well as safety profile of isoquercetin (and parent compound quercetin), the planned sequential dosing cohorts for the clinical phase II trial are 500mg and1000 mg once daily.

Absorption, Metabolism, and Bioavailability

A number of clinical studies have investigated the metabolic fate of quercetin and its glucosides. Isoquercetin is better absorbed than quercetin aglycone, possibly due to increased stability at low pH.²³ The pharmacokinetic study we conducted in healthy adults (isoquercetin 1000 mg capsules) AUC was 1714 and T ½ of 8.23 hours. Isoquercetin undergoes deglycosylation by an extracellular β -glycosidase on the brush border of enterocytes yielding the aglycone.^{24,25} Although the absorption of quercetin and quercetin glucosides differ, all forms of quercetin are metabolized both in the enterocyte and liver and circulate as similar glucuronated, sulfated, and methylated conjugates.²⁶⁻²⁸ These conjugates have demonstrated biologic activity ^{2,29,30}.

Distribution

Isoquercetin and its metabolites possess high affinity for serum albumin.³¹ Quercetin metabolites did not accumulate in tissue following four weeks of daily administration to pigs. Only the organs involved in metabolism and excretion such as the small intestine, liver, and kidney, contained higher concentrations than plasma³². The elimination of absorbed quercetin follows a biphasic profile, likely due to enterohepatic recirculation following elimination of quercetin metabolites in bile.^{31,33}

Excretion

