5 TREATMENT PLAN

Treatment will be administered on an outpatient basis. Expected toxicities and potential risks as well as dose modifications for isoquercetin are described in Section 6 (Expected Toxicities and Dosing Delays/Dose Modification).

Phase	Agent*	Isoquercetin Dose	Route	Schedule	Cycle
Phase II	Isoquercetin (IQC- 950AN) 250mg	Cohort A: 500 mg or Cohort B: 1000 mg	Oral capsules	Cohort A: 2 capsules once daily Cohort B: 4 capsules once daily	28 days
Phase III	Isoquercetin (IQC- 950AN) or Placebo	Cohort C: TBD or Cohort D: Placebo	Oral capsules	Once daily (TBD)	28 days

*All capsules (placebo and isoquercetin) include ascorbic acid 62 mg and niacin 5 mg.

Phase II

Cohort A: Patients will receive isoquercetin 500 mg once daily (2 capsules). Continued enrollment into the dosing cohort will be based on the safety evaluation of the initial 5 patients. If there are ≥ 1 grade 3 or 4 toxicity (possibly, probably or definitely related to isoquercetin), then decision to enroll an additional cohort of 25 patients will be based on DSMC recommendations. If there are ≥ 3 grade 3 or 4 adverse events (possibly, probably or definitely related to isoquercetin), the decision to proceed with enrollment into cohort B will be based on PSMC.

Cohort B: Patients will receive isoquercetin 1000 mg once daily (4 capsules). Similar to cohort A, continued enrollment will be based on the absence of attributable significant toxicities.

For both cohorts A and B, lower extremity ultrasound will be performed at end of treatment visit. Baseline D-dimer and correlative labs will be drawn at Day 1 and at end of treatment visit. Patients will be followed for survival after completion of end of treatment visit.

Phase III

Following the completion of the phase II portion, enrolled patients will be randomized 1:1 to Arm C (isoquercetin) or Arm D (placebo). The dose for Arm C will be determined after evaluation of the Phase II portion of the trial. The protocol will be amended when the decision is made whether to proceed to Phase III and what dose to use for Arm C. The study will be double-blinded to treatment arm. Lower extremity ultrasound will be performed at end of treatment. Baseline D-dimer and correlative labs will be drawn at Day 1 and at end of treatment. Patients will be followed for survival after completion of end of treatment assessment.

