- Fine and Graey regression modelling will be performed to assess the influence of chemotherapy, blood counts, growth factors, ECOG performance status on VTE risk.
- Quality of Life (QOL) will be assesses using EORTC QLQ-30 version 3 which is an internationally validated and widely utilized questionnaire.⁵⁷ Scoring is based on responses to 30 questions dealing with functional quality and symptom burden. The questionnaire will be completed at baseline visit and end of treatment assessments. All are reported on a range 0-100; a high score represents a high level of functioning and QOL. We will analyze the data using analysis of variance techniques if the QoL has constant variance across groups (based on VTE rates and treatment groups). If not, we will use the Kruskal-Wallis test based on ranked QoL scores. If the questionnaire developers provide guidelines for scoring in the presence of missing data, we will

follow those guidelines. Alternatively, we will tally the number of questionnaires for which a particular data item is missing.

- Correlation between isoquercetin dose, plasma PDI inhibitory activity, and reduction in D-dimer or VTE incidence
- Cumulative incidence of VTE according to Khorana score³⁷
- At completion of phase II portion, we will compare the cumulative incidence of VTE of all 60 patients enrolled with similar historical population. As described above the overall cumulative incidence of VTE with similar inclusion criteria and design was 11%. We hypothesize the cumulative incidence of VTE in the phase II cohort will be 4%. Based on these assumptions, the power for this comparison is 80% (N=60 with a 1-sided alpha of 0.1 comparing 4% to historical 11% cumulative incidence rate using a Fisher exact test.)

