Very poor

Excellent

Sample (Plasma) Shipment Report 14-114: Randomized, placebo-controlled, double-blind phase II/III trial of oral isoquercetin to prevent venous thromboembolic events in cancer patients.

Medical Center:				
Patient ID and Initials:				
Collection Date: ////				
Time of draw:	Number Samples drawn: Number Samples sent: Number Samples stored:			
Select the Appropriate Visit: Screening/Pre-treatment visit Day 56 (± 5 days) or End of Study treatment				
Completed By:]			
Comments:				

NOTE: Please see attached study calendar and a detailed instruction about each sample day (visit).

Contact Study Coordinator at Medical Center: ______ Phone: _____ Email: _____

This complete form and samples should be mailed to the above address. Samples should be shipped Monday-Thursday only to ensure samples will still be viable upon receipt. Please email the study team at BIDMC the day the shipment is sent out. Thank you!

Quercegen Pharma. 2015-10-29 rev 1

The contents of IQC-950AN capsules can be mixed with a small amount of food to aid in patient compliance. Based on the dissolution profile of the capsules we can expect that capsule contents are released in the stomach, and the stability of IQC-950AN is expected to be good in the stomach. The capsule contents are light yellow colored and the powder is lightly acidic with an otherwise neutral to slightly bitter taste. The capsules can be opened and the contents mixed with a small portion of soft food. The capsules are "locking", but not sealed, so they can be opened with some twisting and pulling over the food however it is recommended that the opening and emptying be performed for the subject as the capsules are tightly filled and assuring full emptying is important.

The contents are not strong-tasting so it is not necessary to make extra efforts to mask the taste. It is recommended to mix the capsule contents with an already acidic soft-food as this will blend well with the taste. It is not recommended to disperse in a liquid because of low solubility and possibility of powder sticking to container walls.

Since the capsule contents are yellow colored, it is recommended to use a yellowish soft-food which is readily available such as puree of carrots or pumpkin puree, or a darker soft food such as prune puree. However, for dosing consistency a single option or fewer options are recommended.

Suggested instructions;

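### The end-of-treatment plasma sample has no stated time relative to the last dose, and the objective on plasma concentration has no listed assay, which weakens the secondary PDI-inhibition/D-dimer correlation

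*Combined protocol and SAP*

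**What the plan says.** Section 1.3 lists a secondary objective: "To investigate the association between isoquercetin plasma concentrations, inhibition of protein disulfide isomerase activity, and reduction in D-dimer". The matching item in section 14.2 is "Correlation between isoquercetin dose, plasma PDI inhibitory activity, and reduction in D-dimer or VTE incidence". It names dose rather than concentration, and gives no model and no sampling time.

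Section 8.1 lists the assays: tissue factor bearing microparticles, plasma PDI-inhibitory activity, D-dimer, coagulation substrates of PDI and, at one site, platelet aggregometry. No isoquercetin or metabolite concentration is among them. The further testing allowed on stored plasma covers thrombosis risk factors and coagulation markers.

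On timing, section 5 says of phase II: "Baseline D-dimer and correlative labs will be drawn at Day 1 and at end of treatment visit". Phase III has the same two time points. The plasma shipment report (Appendix E) describes the second one as "Day 56 (± 5 days) or End of Study treatment". Section 9 adds: "All assessments must be performed prior to administration of any study medication". The sentence before it concerns baseline evaluations, and the sentence after it gives a general window for all study assessments.

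On the drug, section 2.1 reports for 1000 mg capsules a median peak of 4.45 µM "with a half-life of 8.2 hours", an in vitro IC50 of 3–10 µM, and a peak that "was associated with 67% inhibition of PDI activity in plasma at 4 hours". The only scheduled post-dose draw is optional, at one site, 4 hours after the first dose.

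**The concern.** Plasma PDI inhibition should follow plasma level, and the level falls quickly with an 8-hour half-life. If the end-of-treatment sample may be taken a few hours after that day's capsules in one patient, before dosing in another and days after the last capsule in a third, part of the between-patient spread in measured inhibition is timing.

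D-dimer change is meant to reflect eight weeks of treatment. Correlating it with a value that depends on the hour of the draw adds noise to one side. That generally pulls a correlation toward zero, and a weak result could then not be read as evidence about the mechanism.

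The concentration part of the objective has a separate problem. As written, it has no measurement behind it and no analysis that uses it.

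**Working it through.** **No design figure to reproduce.** The plan gives no sample size, power or precision for this objective. The check is an illustration from the protocol's own pharmacokinetic figures.

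**Inputs.** From section 2.1: peak 4.45 µM and half-life 8.2 h (1000 mg capsules), IC50 3–10 µM, 67% inhibition at 4 h. From section 7.1.1: half-life 9 h and peak 3.5 µM (500 mg chews), used only to give a range.

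**Assumptions not in the documents.** Single-exponential decline counted from the peak, once-daily steady state, and one-site inhibition.

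**Formulas.** Fraction left = 2^(−t/half-life). Steady-state factor = 1/(1 − 2^(−24/half-life)), which is 1.15 at 8.2 h and 1.19 at 9 h. Inhibition = C/(C + IC50).

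For example, at 24 h with 8.2 h: 2^(−24/8.2) = 0.132; 4.45 × 0.132 × 1.15 ≈ 0.67 µM; inhibition 0.67/(0.67 + 10) = 6% to 0.67/(0.67 + 3) = 18%.

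| Hours | Fraction of peak left (8.2 h; 9 h) | Level from 4.45 µM at steady state | Inhibition, IC50 10 to 3 µM |
|---|---|---|---|
| 24 | 13%; 16% | 0.67–0.83 µM | 6–22% |
| 28 | 9%; 12% | 0.48–0.61 µM | 5–17% |
| 48 | 1.7%; 2.5% | 0.09–0.13 µM | 1–4% |
| 72 | 0.2%; 0.4% | 0.01–0.02 µM | under 1% |
| 120 | 0.004%; 0.010% | under 0.001 µM | about 0 |

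From the 3.5 µM peak, the 24-hour level is 0.53–0.65 µM.

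**Check against the reported 67%.** At 4.45 µM the curve gives 4.45/14.45 = 31% to 4.45/7.45 = 60%, so the quoted IC50 range does not reproduce 67%. Solving for the IC50 that does: 4.45 × 0.33/0.67 = 2.19 µM. The 24-hour value is then 0.67/(0.67 + 2.19) ≈ 23–24%. If the peak falls 4 h after the dose, only 20 h of decline precede the next dose: 4.45 × 2^(−20/8.2) = 0.82 µM, times 1.15 = 0.94 µM, and 0.94/(0.94 + 2.19) = 30%. Across these variants, pre-dose inhibition for the 1000 mg dose is roughly 6–30%.

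**What this means for two adherent patients.** On the calibrated curve, a patient sampled 4 h after dosing shows 67% and one sampled just before the next dose shows about 24–30%. That is a two- to threefold difference due only to the clock.

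**Can a gap of days arise?** "The capsules will be packaged as a 30 day supply", and the second bottle is dispensed at Day 29, so it covers Days 29–58. If first-bottle leftovers have been returned, a visit on Day 61 (56 + 5) falls 3 days after the last capsule. Capsules carried over from the first bottle would close most of that gap. Early stopping is a second route, because no interval is set between the last capsule and the end-of-treatment visit.

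**Objective against measurement.** Section 1.3 names concentration, PDI inhibition and D-dimer. Section 8.1 measures the last two. Section 14.2 analyses dose, PDI activity and D-dimer or VTE.

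**Data already collected.** The drug diary has date and time for each dose. The shipment report has collection date and time of draw. Hours since last dose can be computed from these, but no analysis uses it.

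**The case against.** The calendar sentence, read where it stands, most naturally refers to baseline, and nothing tells patients to hold their capsules on the visit day. An ordinary visit a few hours after dosing is allowed. The Day 56 window is ±5 days, because the general ±7 days applies only where nothing else is noted. With two 30-day supplies many patients will still be taking drug at the visit. All of this stands: a pre-dose or late sample is possible but not prescribed. It does not remove the problem, because the baseline-only reading leaves the second sample with no timing rule.

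A pre-dose trough is a legitimate exposure measure. That also stands, but it requires the plan to say that the sample is a trough. PDI activity and D-dimer are both assayed and dose is known, so the section 14.2 correlation can be run. Only the concentration part of the objective is without a measurement.

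The decay model is crude. Section 2.1 describes biphasic elimination with likely enterohepatic recirculation, so the late values are approximate.

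The optional 4-hour draw offers little cover. It follows the first dose only, at one site, and section 8.1 assigns it to aggregometry, although the Appendix C checklist calls it correlative plasma.

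**Conclusion.** The point holds for the secondary PDI-inhibition/D-dimer correlation. The end-of-treatment sample is not tied to the last dose. On the protocol's own half-life, about 13% of peak is left at 24 hours and under 2% at 48 hours, so measured inhibition will partly reflect hours since the last capsule. How much this weakens the correlation depends on the spread of draw times, which the documents do not give. The figures rest on single-exponential decline and a simple inhibition curve. In addition, the concentration part of the objective has no assay and no matching analysis.

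Three stronger conclusions might be inferred and are not supported:

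- **Inhibition near zero in the second sample.** A trough is reduced, at roughly 6–30%, but not absent. Values close to zero apply only from about 48 hours.
- **A biased phase II D-dimer decision because the sample may be off drug.** That would need D-dimer to rebound within hours or days of the last capsule, and the documents give no such kinetics.
- **A mandatory post-dose draw is needed.** A 4-hour sample is one option with its own burden. Section 5 already expects some patients not to stay for it.

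**What to change.** 1. State in section 9 whether the pre-medication sentence applies to the end-of-treatment correlative sample or to baseline only.
2. Derive hours since last dose for each end-of-treatment sample, from the last dose in the diary and the draw date and time on the shipment report. Include it as a covariate in the section 14.2 correlation of PDI-inhibitory activity with D-dimer reduction. Fix the form of the term in advance, since decline is not linear in time.
3. Add a sensitivity analysis, not an exclusion, for samples drawn well beyond one dosing interval. Section 5.2.1 allows a dose to be taken up to four hours late, so any cut should lie beyond 24 + 4 = 28 hours. Otherwise compliant trough samples would be set apart.
4. Reconcile section 1.3 with section 14.2, either by rewording the objective to dose and PDI activity or by naming a concentration assay on the stored plasma.

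Items 1 to 3 need wording, a small data derivation and one extra model term. They need no new form and no extra blood. Item 4 costs only wording if the objective is changed, or laboratory work if an assay is added.
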